### **3.4. Missing Data and Outliers**

#### **3.4.1. Missing Data**

In general, missing data will not be imputed unless methods for handling missing data are specified.

For missing last dosing date of study drug, imputation rules are described in Section [3.6.1](#). The handling of missing or incomplete dates for adverse event (AE) onset is described in Section [7.1.5.2](#), and for prior and concomitant medications in Section [7.4](#)

For analyses of categorical HCV RNA data, missing posttreatment HCV RNA data will have the missing data imputed. Missing on-treatment HCV RNA will have missing data imputed up to the time of the last dose (for on-treatment displays). If the study day associated with the last dosing date of any study drug is greater than or equal to the lower bound of a visit window, and the value at the visit is missing, then the value will be imputed. If the study day associated with the last dosing date is less than the lower bound of a visit window then the on-treatment value at that visit will remain missing.

If a HCV RNA data point is missing and is preceded and followed in time by values that are “< lower limit of quantification (LLOQ) target not detected (TND),” then the missing data point will be set to “< LLOQ TND.” If a data point is missing and preceded and followed by values that are “< LLOQ detected,” or preceded by “< LLOQ detected” and followed by “< LLOQ TND,” or preceded by “< LLOQ TND” and followed by “< LLOQ detected,” then the missing value will be set to “< LLOQ detected.” In these situations the data point will be termed a bracketed success; otherwise, the data point will be termed a bracketed failure (ie, ≥ LLOQ detected). If a data point is missing and is not bracketed, the missing data point will also be termed a failure (ie, ≥ LLOQ detected) except for SVR24, which will be imputed according to SVR12 status. Success for SVR12 who have no further HCV RNA measurements collected will be counted as a success for SVR24 due to the high correlation between these 2 endpoints.

For the analyses of continuous HCV RNA efficacy data, when and only when a missing HCV RNA value is imputed as < LLOQ TND or < LLOQ detected according to the imputation rule described above, the corresponding continuous value will be imputed to LLOQ – 1 IU/mL. No other imputation will be performed for continuous HCV RNA data.

For health-related quality of life data including SF-36, CLDQ-HCV, FACIT-F, and WPAI: Hep C, missing data at on-treatment visits, and posttreatment follow-up Week 12 (FU-

12) visit will not be imputed. For SF-36, if there are multiple responses to an item, the response will be set to missing.

### **3.4.2. Outliers**

Outliers will be identified during data management and data analysis process, but no sensitivity analyses will be conducted. All data will be included in the data analysis.

## **3.5. Data Handling Conventions and Transformations**

By-subject listings will be presented for all subjects in the Safety Analysis Set and sorted by subject ID number, visit date, and time (if applicable) unless otherwise specified. Data collected on log forms, such as AEs, will be presented in chronological order within subject.

Age (in years) on the date of the first dose of study drug and sex at birth will be used for analyses and presentation in listings.

If a subject was not dosed with study drug at all, then the date the informed consent was signed will be used instead of the first dose date of study drug.

Non-pharmacokinetic (PK) data that are continuous in nature but are less than the lower limit of quantitation or above the upper limit of quantitation will be imputed as follows:

- A value that is one unit less than the limit of quantitation will be used for calculation of descriptive statistics if the datum is reported in the form of “ $< x$ ” (where  $x$  is considered the limit of quantitation). For example, if the values are reported as  $< 50$  and  $< 5.0$ , values of 49 and 4.9, respectively, will be used for calculation of summary statistics. An exception for this rule is any value reported  $< 1$ . For the values reported as  $< 1$  or  $< 0.1$ , value of 0.9 or 0.09 will be used for calculation of summary statistics.
- A value that is one unit above the limit of quantitation will be used for calculation of descriptive statistics if the datum is reported in the form of “ $> x$ ” (where  $x$  is considered the limit of quantitation). Values with decimal points will follow the same logic as above.
- The limit of quantitation will be used for calculation of descriptive statistics if the datum is reported in the form of “ $\leq x$ ” or “ $\geq x$ ” (where  $x$  is considered the limit of quantitation).

COBAS® AmpliPrep/COBAS® TaqMan® HCV Quantitative Test, v2.0 will be used to determine HCV RNA results in this study. The lower limit of quantitation (LLOQ) of the assay is 15 IU/mL.

When the calculated HCV RNA value is within the linear range of the assay, then the result will be reported as the “ $<<$  numeric value $>>$  IU/mL.” This result will be referred to in this document as the numeric result or as “ $\geq$  LLOQ detected” for categorical result.

When HCV RNA is not detected, the result is reported as “No HCV RNA detected” or “target not detected”. This result will be referred to in this document as “< LLOQ target not detected” or “< LLOQ TND.”

When the HCV RNA IU/mL is less than LLOQ of the assay, the result is reported as “< 15 IU/mL HCV RNA detected”. This result will be referred to in this document as “< LLOQ detected.”

The overall category of HCV RNA < LLOQ includes “< LLOQ TND” and “< LLOQ detected.”

For numerical HCV RNA data, values below LLOQ will be set to the LLOQ – 1 IU/mL (ie, 14 HCV RNA IU/mL). HCV RNA values returned as “No HCV RNA detected” will also be set to 14 IU/mL.

For selected analyses, HCV RNA data (IU/mL) will be transformed to the logarithmic (base 10) scale ( $\log_{10}$  IU/mL).

Natural logarithm-transformation will be used for plasma/blood concentrations and analysis of PK parameters. Plasma concentration values that are below the limit of quantitation (BLQ) will be presented as “BLQ” in the concentration data listing. Values that are BLQ will be treated as 0 at predose time points, and one-half the value of the lower limit of quantitation (LLOQ) at postbaseline time points.

The following conventions will be used for the presentation of summary and order statistics:

- If at least 1 subject has a concentration value of BLQ for the time point, the minimum value will be displayed as “BLQ.”
- If more than 25% of the subjects have a concentration data value of BLQ for a given time point, the minimum and Q1 values will be displayed as “BLQ.”
- If more than 50% of the subjects have a concentration data value of BLQ for a given time point, the minimum, Q1, and median values will be displayed as “BLQ.”
- If more than 75% of the subjects have a concentration data value of BLQ for a given time point, the minimum, Q1, median, and Q3 values will be displayed as “BLQ.”
- If all subjects have concentration data values of BLQ for a given time point, all order statistics (minimum, Q1, median, Q3, and maximum) will be displayed as “BLQ.”

### **3.6. Visit Windows**

#### **3.6.1. Definition of Study Day**

Study day is the day relative to the date of the first dose of study drug. Study Day 1 will be defined as the day of first dose of study drug administration.

Study day will be calculated from the date of first dose of study drug administration and derived as follows:

- For postdose study days: Assessment Date – First Dose Date + 1
- For days prior to the first dose: Assessment Date – First Dose Date

The last dose date will be the end date on study drug administration eCRF for the record where the “subject permanently discontinued” flag is ‘Y’. The last dose date will be defined as the maximum of the last dose dates of the study drugs. If there are subjects for whom the date of last study drug is unknown due to the reason that the subject was lost to follow-up and not able to be contacted, the date of last dose will be estimated using the maximum of nonmissing study drug start or stop dates, visit dates, and laboratory collection dates (posttreatment visits and unscheduled visits are not included).

### 3.6.2. Analysis Windows

Subject visits might not occur on protocol-specified days. Therefore, for the purposes of analysis, observations will be assigned to analysis windows.

In general, the baseline value will be the last nonmissing value on or prior to the first dose date of study drug.

HCV RNA, vital signs, and safety laboratory data collected up to the last dose date + 3 days are considered to be on-treatment data and HCV RNA, vital signs, and safety laboratory data collected after the last dose date + 3 days are considered posttreatment data. The analysis windows for on-treatment HCV RNA, vital signs and safety laboratory data are provided in [Table 3-1](#).

**Table 3-1. Analysis Windows for On-treatment HCV RNA, Vital Signs and Safety Laboratory Data**

Nominal Visit	Nominal Day (Lower Limit, Upper Limit) 8-Week Groups	Nominal Day (Lower Limit, Upper Limit) 12-Week Groups	Nominal Day (Lower Limit, Upper Limit) 24-Week Groups
Baseline	1 (none, 1)	1 (none, 1)	1 (none, 1)
Week 2	14 (12, 21)	14 (12, 21)	14 (12, 21)
Week 4	28 (22, 35)	28 (22, 35)	28 (22, 35)
Week 6	42 (36, 49)	42 (36, 49)	42 (36, 49)
Week 8	56 (50, $\geq$ 57)	56 (50, 70)	56 (50, 70)
Week 12	NA	84 (71, $\geq$ 85)	84 (71, 98)
Week 16	NA	NA	112 (99, 126)
Week 20	NA	NA	140 (127, 154)
Week 24	NA	NA	168 (155, $\geq$ 168)

HCV RNA, vital sign, and safety laboratory data collected after the last dose date + 3 days will be assigned to the posttreatment follow-up (FU) visits. Visit windows will be calculated from the last dose date (ie, FU Day = collection date minus the last dose date) as shown in [Table 3-2](#).

**Table 3-2. Analysis Windows for Posttreatment HCV RNA, Vital Signs and Safety Laboratory Data**

Nominal FU a Visit	HCV RNA			Vital Signs and Safety Laboratory Data b		
	Nominal FU Day	Lower Limit	Upper Limit	Nominal FU Day	Lower Limit	Upper Limit
FU-4	28	21	69	28	4	30
FU-12	84	70	146	NA	NA	NA
FU-24	168	147	210	NA	NA	NA

a. FU-x visit = posttreatment Week-x follow-up visit.

b. Vital signs and safety labs will only be summarized for the FU-4 visit (up to 30 days after last dose).

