6.3. Treatment Assessments

6.3.1. Week 2 (\pm 3 days): Group 1, 2, and 3

The following procedures/assessments are to be completed at the end of Week 2:

- Obtain vital signs
- Assessment of AEs and concomitant medications

- Obtain blood samples for:
 - Hematology
 - Chemistry
 - HCV RNA
 - Viral sequencing/phenotyping
 - Sparse PK sample
- Assess adherence with study drug dosing regimen including pill count

6.3.2. Week 4 (\pm 3 days): Group 1, 2, and 3

The following procedures/assessments are to be completed at the end of Week 4:

- Obtain vital signs
- Assessment of AEs and concomitant medications
- Conduct pregnancy prevention counselling
- Obtain blood samples for:
 - Hematology
 - Chemistry
 - HCV RNA
 - Viral sequencing/phenotyping
 - Sparse PK sample
 - Serum β -hCG pregnancy test for females of childbearing potential only
 - HIV-1 RNA and CD4 cell count will only be collected and analyzed for HIV co-infected subjects
 - HBV DNA (only in subjects who are HBcAb+ at Screening)
- Assess adherence with study drug dosing regimen including pill count
- Dispense study drug as directed by the IWRs

6.3.3. Week 6 (\pm 3 days): Group 1, 2, and 3

The following procedures/assessments are to be completed at the end of Week 6:

- Obtain vital signs
- Assessment of AEs and concomitant medications
- Obtain blood samples for:
 - Hematology
 - Chemistry
 - HCV RNA
 - Viral sequencing/phenotyping
 - Sparse PK sample
 - Intensive PK (for subjects who have consented)
 - Hemodialysis PK (for subjects who have consented)
- Assess adherence with study drug dosing regimen including pill count

6.3.4. Week 8 (\pm 3 days): Group 2 and 3 (For Group 1 Week 8, see End of Treatment Visit)

The following procedures/assessments are to be completed at the end of Week 8 for Groups 2 and 3 only:

- Obtain vital signs
- Assessment of AEs and concomitant medications
- Conduct pregnancy prevention counselling
- Obtain blood samples for:
 - Hematology
 - Chemistry
 - HCV RNA
 - Viral sequencing/phenotyping

- Sparse PK sample
- Serum β-hCG pregnancy test for females of childbearing potential only
- HIV-1 RNA and CD4 cell count will only be collected and analyzed for HIV co-infected subjects
- HBV DNA (only in subjects who are HBcAb+ at Screening)
- Intensive PK (for subjects who have consented)
- Hemodialysis PK (for subjects who have consented)
- Assess adherence with study drug dosing regimen including pill count
- Dispense study drug as directed by the IWRs

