8.6. Safety Analysis

Safety will be evaluated by assessment of clinical laboratory tests (including HIV-1 RNA and CD4 T-cell count for HCV/HIV co-infection subjects), physical examinations, vital signs measurements at various time points during the study, and by the documentation of AEs.

All safety data collected on or after the first dose of study drug administration up to 30 days after the last dose of study drug will be summarized by treatment group according to the study drug received.

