Appendix 2. Study Procedures Table

Appendix Table 1. Screening/Baseline/ On-Treatment and Post Treatment Study Visits for Group 1

	Screen	Baseline/Day 1 ^a	On-Treatment Week (± 3 Days)				Post-Treatment Week (± 5 Days)		
			2	4	6	8/ET	4	12	24
Informed Consent	X								
Determine Eligibility	X	X							
Medical History	X								
Physical Examination	X	X				X	X	X	X
Height	X								
Weight	X	X				X			
Vital Signs	X	X	X	X	X	X	X	X	X
12-Lead ECG	X	X				X			
AEs/SAE ^b	X	X	X	X	X	X	X	X ^b	X ^b
Concomitant Medications	X	X	X	X	X	X	X		
Pregnancy Prevention Counseling	X	X		X		X	X		
Health-Related Quality of Life ^c		X				X		X	
Review of Study Medication Compliance			X	X	X	X			
Study Drug Dispensing ^d		X		X					
Hematology, Chemistry	X	X	X	X	X	X	X	X	X
Coagulation Tests	X	X				X			
HCV RNA	X	X	X	X	X	X	X	X	X
Viral Sequencing/Phenotyping ^e		X	X	X	X	X	X	X	X
Sparse PK			X	X	X	X			
Intensive PK ^{g, h}					X ^h	X ^h			

	Screen	Baseline/Day 1 ^a	On-Treatment Week (± 3 Days)				Post-Treatment Week (± 5 Days)		
			2	4	6	8/ET	4	12	24
Hemodialysis PK ^{g,i}					X ⁱ	X ⁱ			
Serum β -hCG Pregnancy Test ^j	X	X		X		X	X		
Serum Drug Screen	X								
HCV & IL28B Genotyping	X								
HCV, HIV, HBV Serology	X								
HBV DNA ^k		X		X		X	X	X	X
HbA1c	X								
Fibrotest [®]	X								
Archive Sample ^f		X				X			
Pharmacogenomic Sample ^f		X							
CD4 Cell Count ^l	X	X		X		X	X		
HIV-1 RNA ^l	X	X		X		X	X		

a Baseline/Day 1 assessments must be performed prior to dosing

b Only SAEs will be collected at post-treatment Weeks 12 and 24.

c Health Related Quality of Life (HRQoL) Surveys (e.g., SF-36, CLDQ-HCV, FACIT-F and WPAI) will be conducted for all subjects where the surveys are available at Day 1, Week 8, ET (if applicable), and posttreatment Week 12.

d The IWRS will provide direction on the specifics of each subject's study drug dispensing

e. Plasma samples will be collected for possible viral resistance testing and other virology studies

f Subjects may opt out of archive/pharmacogenomics sample collection.

g Only for subjects who have provided consent for this sample and testing.

h Intensive PK evaluations will be assessed at the following timepoints: 0 (pre-dose -5 minutes), 0.25, 0.5, 1, 2, 4, 6 ,8, 10, and 12 hours post dose once either on Week 6 or 8, per investigator discretion.

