##### **4.2.1. Duration of Exposure to Study Drug**

Total duration of exposure to study drug will be defined as last dose date minus first dose date plus 1, regardless of any temporary interruptions in study drug administration, and will be expressed in weeks using up to 1 decimal place (eg, 4.8 weeks). The total duration of exposure to study drug will be summarized using descriptive statistics (n, mean, SD, median, Q1, Q3, minimum, and maximum) and using the number (ie, cumulative counts) and percentage of subjects exposed through the following time periods: Baseline (Day 1), Week 4 (Day 28), Week 8 (Day 56), Week 12 (Day 84), Week 16 (Day 112), Week 20 (Day 140), and Week 24 (Day 168). A 3-day window is applied to the last planned on-treatment visit to match with the protocol-specified visit window, i.e. number of subjects exposed through Week 8 will be calculated as the number of subjects who were exposed to study drug for at least 53 days. Number of subjects exposed through week 12 will be calculated as the number of subjects who were exposed to study drug for at least 81 days. Number of subjects exposed through week 24 will be calculated as the number of subjects who were exposed to study drug for at least 165 days.

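### Two SAP window limits, the Week 2 start on day 12 and the FU-4 safety end on day 30, leave out visit days that the protocol permits

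*SAP*

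**What the plan says.** Protocol Appendix 2 heads the visit columns "On-Treatment Week (± 3 Days" and "Post-Treatment Week (± 5 Days", each closing with a bracket. Protocol 6.3.1 fixes Week 2 without a study-day number: "The following procedures/assessments are to be completed at the end of Week 2".

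The SAP turns weeks into days. In SAP 3.6.1, "Study Day 1 will be defined as the day of first dose of study drug administration". For the posttreatment period, SAP 3.6.2 uses "FU Day = collection date minus the last dose date". Table 3-1 ends baseline on day 1 and gives Week 2 a nominal day of 14 with limits 12 and 21, in all three duration groups. Table 3-2 has two separate FU-4 windows: days 21 to 69 for HCV RNA, and days 4 to 30 for vital signs and safety laboratory data. FU-12 and FU-24 are marked NA for the safety data, and footnote b reads "Vital signs and safety labs will only be summarized for the FU-4 visit (up to 30 days after last dose".

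The day-30 limit follows a rule in Protocol 8.6, under which safety data "up to 30 days after the last dose of study drug will be summarized by treatment group". SAP 7.2 repeats it for laboratory summaries.

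Under SAP 3.4.1, a missing categorical HCV RNA value at an on-treatment visit is imputed if the last dose falls on or after the lower limit of that visit's window. It becomes a success only if values below LLOQ come before and after it. Otherwise it becomes a failure, that is, at or above LLOQ.

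**The concern.** A visit made on a day the protocol allows should land in the analysis window for that visit. Where it does not, observed data leave the by-visit tables although the site did nothing wrong.

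Two displays are at stake. Week 2 is the first on-treatment HCV RNA time point, and it feeds the secondary endpoint of HCV RNA below LLOQ by visit. FU-4 is the only posttreatment time point at which laboratory data and vital signs are summarised. Hemoglobin and reticulocytes are among the analytes summarised and plotted by visit (SAP 7.2.1), and Protocol 1.5 names reduced red-cell counts as a risk in this population.

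**Working it through.** **Convention.** The protocol gives weeks and the SAP gives days, so the conversion must be settled first. SAP 4.2.1 applies the 3-day tolerance to planned treatment lengths and counts a subject as exposed through Week 8 if "exposed to study drug for at least 53 days". Taking 7 × week − 3 reproduces all three of its thresholds: 56 − 3 = 53, 84 − 3 = 81 and 168 − 3 = 165. The SAP therefore works with nominal day = 7 × week, which is also what Table 3-1 shows.

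**Comparison.** Permitted days are 7w ± 3 on treatment, counted as study days, and 7w ± 5 after treatment, counted from the last dose.

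| Visit | Permitted days | SAP window | Permitted days outside |
|---|---|---|---|
| Week 2 | 11–17 | 12–21 | 11 |
| Week 4 | 25–31 | 22–35 | none |
| Week 6 | 39–45 | 36–49 | none |
| Week 8 | 53–59 | 50–70 (open-ended in Group 1) | none |
| Week 12 | 81–87 | 71–98 (open-ended in Group 2) | none |
| Week 16 | 109–115 | 99–126 | none |
| Week 20 | 137–143 | 127–154 | none |
| Week 24 | 165–171 | 155 onward | none |
| FU-4, HCV RNA | 23–33 | 21–69 | none |
| FU-12, HCV RNA | 79–89 | 70–146 | none |
| FU-24, HCV RNA | 163–173 | 147–210 | none |
| FU-4, vital signs and safety labs | 23–33 | 4–30 | 31, 32, 33 |

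Two limits fall short: 1 of 7 permitted days at Week 2 and 3 of 11 at FU-4 for safety data. Days 2 to 11 belong to no on-treatment window, whereas from day 12 on each window starts the day after the previous one ends.

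**What happens to a day-11 visit.** Its laboratory values and vital signs are absent from the Week 2 by-visit summary. Its HCV RNA result is not a Week 2 value, so Week 2 is missing. If the subject is still dosing on day 12 or later, SAP 3.4.1 calls for imputation. Inclusion criterion 4 requires HCV RNA at or above LLOQ at screening, so baseline is not expected to be below it. Two readings follow.

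- If only windowed values can bracket, the preceding value is baseline and Week 2 is imputed as at or above LLOQ, even when day 11 was observed below LLOQ.
- If the day-11 value can bracket, and it and the next value are both below LLOQ, Week 2 is a bracketed success.

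SAP 3.4.1 speaks of values before and after in time and does not restrict them to windowed ones. SAP 6.2.2 assigns visit values by window. Neither says which reading applies.

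**What happens to a visit on FU days 31 to 33.** HCV RNA from that visit is FU-4. Hemoglobin, ALT and blood pressure from the same visit are in no window and enter no by-visit summary.

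**The case against.** The strongest defence is that day 30 is no slip. Protocol 8.6 limits summarised safety data to 30 days after the last dose, the protocol uses the same limit for treatment-emergent events and graded laboratory abnormalities, SAP 7.2 repeats it, and footnote b states it openly. That stands: the limit is deliberate. What remains is that the rule does not fit the protocol's own tolerance of 5 days at posttreatment Week 4, and the only posttreatment by-visit safety summary inherits the mismatch.

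A second defence is that the day-11 gap depends on convention. If the end of Week 2 is read as day 15, the permitted range is 12 to 18 and nothing is lost. The protocol does not exclude this. The SAP's own nominal day 14 and the thresholds in SAP 4.2.1 point the other way, so the gap exists on the SAP's terms.

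Third, the values are not lost. A reader might infer that compliant data are discarded, but SAP 7.2 and 7.3 list all laboratory results and vital signs by subject. Day-11 laboratory values still count towards graded abnormalities and the hemoglobin thresholds, which use any postbaseline value up to 30 days after the last dose. Values on days 31 to 33 do not enter those counts, but that follows from the 30-day rule and not from the window table.

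A reader might also infer that an observed day-11 result below LLOQ is bound to be recoded as a failure. The text does not support that, because one of the two readings of the bracketing rule avoids it.

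**Conclusion.** The point holds for two limits and no further; it would be wrong to conclude that the SAP windows are narrower than the protocol's in general. On the SAP's convention of 7 days per week, a permitted day-11 visit falls outside Week 2, and permitted visits on FU days 31 to 33 fall outside FU-4 for vital signs and laboratory data. The effect is confined to by-visit summaries and to the secondary, descriptive Week 2 HCV RNA display. The HCV RNA windows for FU-4, FU-12 and FU-24 contain every permitted day, so SVR4, SVR12 and SVR24 are not touched.

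The size can be stated only in days: 1 of 7 and 3 of 11. Reading these as 14% and 27% of subjects would require visits to be spread evenly over the permitted range, and the documents give no visit distribution. Severity is minor. The Week 2 limit is the clearer of the two, since no rule in either document explains a start on day 12.

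**What to change.** **Week 2 (Table 3-1).** Set the lower limit to day 11 or earlier. Day 2 would make the window contiguous with baseline. It has one side effect: SAP 3.4.1 ties imputation to the lower limit, so a subject who stops between days 2 and 11 with no value in the window would then be imputed at Week 2 instead of left missing. Day 11 is the smallest change that covers the permitted range.

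**FU-4 safety data (Table 3-2).** Extend the upper limit to day 33 for the by-visit vital-sign and laboratory summaries only. Keep the 30-day rule for treatment-emergent events, graded abnormalities and the hemoglobin threshold counts. Amend footnote b and SAP 7.2 to match; otherwise the table and the text would contradict each other. Record the departure from Protocol 8.6 in SAP 7.7, which now says there is none.

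The cost is a few SAP lines, to be settled before the database is finalised. The downside is small: a few by-visit values would lie beyond the 30-day treatment-emergent period.
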